8.4.5 Subject replacement policy

Withdrawn subjects would not be replaced.

8.4.6 Screening failures

Patients who fail to meet the inclusion and exclusion criteria are defined as screening failures. A screening log will be maintained which includes screen failures. The log will document the subject number, subject initials, demographics and the reason(s) for excluding the patient from the study. This log will be kept in the Investigator's Study File.

9 TREATMENT AND STUDY PROCEDURES

9.1 Description of study drug

9.1.1 Treatment for Group 1: Cholestyramine group

Cholestyramine 4g twice daily + Carbimazole 30 mg daily+ Propanolol 40 mg twice daily for 4 weeks

Study treatment consists of cholestyramine powder 4g (1 sachet) twice a day and standard treatment which includes tablet carbimazole 30 mg daily and tablet propanolol 40 mg twice a day to be taken orally for 4 weeks.

The trial dosage of cholestyramine is based on available clinical data and is not considered to cause adverse reactions^{9,12}. The trial dosage for carbimazole is based on available clinical data¹⁶ and in line with the current ATA 2016 hyperthyroid guidelines⁴ and our current local standard practice in treating patients with moderate to severe hyperthyroidism. The trial dosage of propanolol is as per ATA 2016 recommendations to provide symptom relief⁴.

Subjects are instructed to mix cholestyramine powder with 60-180 mls of fluid, to be taken before breakfast and dinner and advised to drink plenty of fluids to prevent constipation. It is recommended to take other drugs one hour before or 4-6 hours after cholestyramine to prevent interference from the powders with absorption. Please refer to drug leaflet attached for full description of cholestyramine. Tablet carbimazole is to be taken whole before, during or after meal at the same time of the day. Propanolol should be taken at the same time daily either before or with meals. Please refer to drug leaflet for more information.

9.1.2 Treatment for Group 2: Prednisolone group

Prednisolone 30 mg daily for week 1, 20 mg daily for week 2, 10 mg daily for week 3 and 5 mg daily for week 4+ Carbimazole 30 mg daily+Propanolol twice daily for 4 weeks

The study treatment for Group 2 consists of tablet prednisolone 30 mg daily for week 1, tapered down to 20 mg daily for week 2, 10 mg daily for week 3 and 5 mg daily for week 4 (total 4 weeks) and standard treatment which includes tablet carbimazole 30 mg daily and tablet propanolol 40 mg twice a day for 4 weeks.

There are no previous clinical trials conducted on adding prednisolone as adjunctive treatment for hyperthyroidism. The trial dosage for tablet prednisolone was selected based on a case series by Ozawa et al. as there were no clinical trials, who added 30 mg of prednisolone to patients who were thyrotoxic and intolerant to thionamides. The dose of prednisolone in his case series of 4 patients were either tapered down within a month or maintained at 30 mg daily less than a month. All patients achieved normal thyroid function in 2-4 weeks and underwent subtotal thyroidectomy successfully¹⁷. We have also used similar doses in clinical practice and found it to be effective. Therefore the starting dose for prednisolone in this trial was chosen at 30 mg daily with a tapering down dose over 4 weeks to to minimize potential side effects of prolonged steroid use. Trial dosage for carbimazole and propanolol is as mentioned above

Subjects are instructed to take the tablets in the morning with or after meals to decrease gastrointestinal upset. Subjects are encouraged not to miss any doses and if they do miss a dose, to take it as soon as possible and if it is almost time for the next dose, skip the missed dose and go back to regular dosing schedule and not to take 2 doses at once. They are advised to avoid alcohol while on prednisolone. Please refer to drug leaflet for more information.

9.1.3 Group 3 Standard treatment group Carbimazole 30 mg daily + Propanolol 40 mg twice daily

Standard treatment group consists of tablet carbimazole 30 mg daily and tablet propanolol 40 mg twice a day for 4 weeks. Please refer to drug leaflet for more information.

9.2 Investigational product supply and handling

9.2.1 Supply, packaging and labeling

Each study drug box will be labeled with the following information:

- 1. Participant's ID
- 2. Drug's name
- 3. Dose
- 4. Instruction on how to use
- 5. Storage condition
- 6. Expiry date
- 7. Pl's name

9.2.2 Storage

The study drug will be stored between 20-25⁰C, protected from moisture and be stored in accordance with the manufacturers' instructions.

The study drug will be kept under adequate security by the investigator and only accessible to authorised study personnel.

9.2.3 Dispensing

Each patient will be dispensed sufficient medication for two weeks of therapy. Upon dispensation, the research pharmacist will write the following in the Investigational Product Dispensing Log: subject ID and initials and date dispensed, the total dose given weekly/monthly and frequency of dosage, total bottles dispensed, batch number and expiry date of product.

9.2.4 Accountability

The investigator will maintain current and accurate record of the receipt, inventory and dispensing, including shipping invoices, of all study supplies. The Investigational Product Accountability Log will include:

- Date received
- Delivery order (D.O.#) reference number and amount received and placed in storage
- Name of study medication and dosage
- Amount currently in storage area
- Label ID number or batch number/Lot number
- Amount dispensed to and returned by each subject, including unique subject identifiers

Accountability logs must be available at any time. Upon completion/termination of the study, unused study drug must be returned to the sponsor for reconciliation and destruction.

9.3 Concomitant medication/treatment

A concomitant medication is any medicatiom, other than the trial product, which is taken during the trial. Details of any concomitant medication must be recorded at visit 1. Changes in concomitant medication must be recorded at each subsequent visit as they occur.

Concomitant medications that are not permitted during the study period

Plasma levels and efficacy of prednisolone may be affected by the concomitant use amphotericin B, anticholinesterase agents, CYP 3A4 inducers (e.g. barbiturates, phenytoin, carbamazepine, and rifampin), CYP 3A4 inhibitors (e.g., ketoconazole, macrolide antibiotics), cyclosporine and digitalis. Lithium, Propylthiouracil, Lugols iodine, Contrast medium are not permited as it will affect the results of the study.

Cautious use of phenylbutazone, warfarin, thiazide diuretics (acidic) as well as tetracycline penicillin G, phenobarbital, thyroid and thyroxine preparations, estrogens and progestins and digitalis as cholestyramine resin may delay or reduce the absorption of these drugs.

9.4 Treatment allocation and randomization

A participant will be randomly allocated to one of the three treatments per random allocation sequence that will be generated by a member of the study team. The allocation ratio is 1:1:1. The random allocation sequence will the Web site Randomization.com be generated by using (http://www.randomization.com). Blocked randomisation will be used. The random allocation sequence will be generated by a member of the study team who will not be involved in the enrolment of subjects and assessment of outcomes. The block size of 6 will be used. The allocation sequence generated will be will be concealed in an opaque sealed envelope with the following information written:

Front page

- 1. Study title
- 2. Site name and code

- 3. Study PI name
- 4. Protocol number
- 5. Sequential randomization number

Inside the randomization envelope

- 1. Study title
- 2. Site name and code
- 3. Study PI name
- 4. Protocol number
- 5. Sequential randomization number
- 6. Subject ID
- 7. Date and time the envelope open
- 8 Signature and name of the person opening the envelope
- 9. Study treatment the patient is allocated to

The identity of the treatment that will be assigned to each subject will only be revealed on the first day of treatment. Principal Investigator and/or Sub Investigator will screen and enrol the subjects. Principal Investigator and/or Sub Investigator will assign the treatment to each subject, according to the allocation sequence.

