8 STUDY DESIGN

8.1 Overall study design

This a multi-center, open-label, randomised, parallel-group study to compare the efficacy of cholestyramine plus standard treatment versus prednisolone plus standard treatment versus standard treatment alone in the treatment of overt hyperthyroidism. The allocation ratio is 1:1:1.

Group 1: Cholestyramine plus standard treatment

Cholestyramine powder 4g BD, Tablet Carbimazole 30 mg OD, Tablet Propanolol 40 mg BD for 4 weeks

Group 2: Prednisolone plus standard treatment

Tablet Prednisolone 30 mg OD for week 1, 20 mg OD for week 2, 10 mg OD for week 3 and 5 mg OD for week 4, Tablet Carbimazole 30 mg OD, Tablet Propanolol 40 mg bd for 4 weeks

Group 3: Standard Treatment alone

Tablet Carbimazole 30 mg OD, Tablet Propanolol 40 mg BD for 4 weeks

8.2 Schematic diagram of study design:

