8.3 Discussion of study design

All hyperthyroid subjects secondary to Graves disease identified at endocrine, endocrine surgery, general medical clinics and medical wards in Hospital Putrajaya, Hospital Queen Elizabeth II and Hospital Ampang will be screened from May 2017/ Upon approval from MREC to 31st December 2017. Potential participants will be invited to a screening visit.

Screening visit

The screening visit consists of providing information about the study, obtaining informed consent and screening assessment. The investigator will further explain the study, answer any questions and seek informed consent. All subjects will provide written informed consent to their participation in the study. The subject will then have a complete history taking, clinical examination and anthropometric measures. They will have their blood sampled, approximately 10 ml for screening tests. Subjects are eligible for the trial, if they comply with the following inclusion and exclusion criteria.

Baseline visit and Randomisation

Subjects eligible for the trial will return for baseline assessment and randomisation. They will be assigned a unique sequentially numbered study identifier according to the order in which he or she is enrolled in the trial.

The subject will then complete the baseline assessment including history taking, clinical examination, anthropometric measures, blood sampling (6 ml) and imaging (if not done previously). Following baseline assessment, subjects will be randomised into either of the 3 treatment groups. A subject will be randomly allocated to one of the three treatments per random allocation sequence that will be generated by a member of the study team.

Duration

The total trial duration is expected to be 7 weeks (1 weeks screening period, 4 weeks intervention period and 2 weeks follow up period). The intervention period for each subject will be 4 weeks. The subject will return at week 2 and week 4 of intervention for safety and compliance assessment and blood sampling (6 ml each visit) for biochemical monitoring. There will be a follow up visit 2 weeks from the end of intervention period to monitor for any adverse effects and complications and a repeat blood sampling (6ml) for biochemical monitoring.

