8.4.1 Inclusion criteria

- 1. Provision of written consent by subject or guardian.
- 2. Subject of either sex, more than 18 years of age
- 3. Subjects with moderate to severe overt hyperthyroidism (caused by Graves' disease).
 - Moderate to severe overt hyperthyroidism is defined as Free T₄>
 1.5 times upper limit of normal reference range and TSH below lower limit of reference range, who are either newly diagnosed or previously diagnosed and receiving ATDs currently.
 - •Graves disease is defined as hyperthyroidism coupled with clinical signs of symmetrical diffuse goiter, thyroid orbitopathy, or diffuse and vascular thyroid on ultrasound or positive TRAb antibody.
- 4. Female patients will either be
 - post-menopausal for > 2 years
 - Women of childbearing potential can be included if surgically sterile or using double contraception with at least one method being barrier contraception. Women of childbearing potential must have a negative pregnancy test at screening and at randomisation. Pregnancy tests will be repeated during each visit.

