8.4.2 Exclusion criteria

- 1. Inability or unwillingness to provide written consent.
- 2. Inability or unwillingness to comply with the requirements of the protocol as determined by the investigator.
- 3. Pregnancy, breastfeeding or use of non-reliable method of contraception.
- 4. Subjects with history of chronic liver disease, chronic renal failure, heart failure, diabetes mellitus
- 5. Subjects with history of peptic ulcer disease, upper gastrointestinal bleeding, diverticulitis or ulcerative colitis.

- 6. Subjects who have recently had live or attenuated virus vaccines
- 7. Subjects with current infection (systemic fungal, active tuberculosis, cerebral malaria, viral hepatitis, HIV)
- 8. Subjects with cataracts and glaucoma
- 9. Subjects with osteoporosis
- 10. Subjects with psychiatric disorders
- 11. Subjects with complete biliary obstruction, bleeding disorders, hypertriglyceridemia (fasting triglyceride levels > 300mg/dL)
- 12. Previous history of adverse reactions to cholestyramine or other bile acid sequestrants
- 13. Previous history of adverse reactions to prednisolone or other steroid compound
- 14. Current use of cholestyramine or prednisolone or other steroid compound
- 15. Participation in another clinical trial and/or receipt of cholestyramine or prednisolone within 4 weeks prior to screening visit.
- 16. Subjects with history of bronchial asthma, bronchospasm, peripheral vascular disease or adverse reactions to propanolol
- 17. Subjects with adverse reactions to carbimazole
- 18. Hypokalemia (serum K^+ <3.5 mmol/L)
- 19. Thyroid storm defined as Burch Wartofsky Score >45

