11.1.2 Baseline visit (Week 0, Visit 2)

- Subjects who are eligible for the study after reviewing both inclusion and exclusion criteria will be called up for a baseline visit no longer than 1 weeks from screening visit.
- 2. Perform baseline measurements of vital signs (BP, HR, Temperature) and anthropometric measurements (Height (cm), Weight (kg) and BMI
- 3. Perform complete medical history and physical examination if not done during screening visit
- 4. Record any concomitant medications
- 5. The following baseline tests will be performed (Total of 6 mls of blood will be sampled). Thyroid function test and TRAb levels will be sent to central lab (Gribbles laboratory) whereas the other tests will be conducted at respective site.
 - a. Free T₄, Free T₃, TSH
 - b. TRAb levels
 - c. UPT (For all women of childbearing age)
 - d. ECG
 - e. ECHO if evidence of thyrotoxic cardiomyopathy
- 6. Complete relevant section/page of the CRF.
- 7. Subject who has fulfilled all inclusion and exclusion criteria and has completed baseline assessment will proceed to randomisation into any of the 3 treatment groups on the **same day**.
- 8. Refer to the study activities table below

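### Section 9.4 discloses one fixed block size of 6 to open-label investigators who enrol and assign, and does not say how envelopes are divided among sites: a minor point with a cheap improvement

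*Combined protocol and SAP*

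**What the plan says.** Section 9.4 specifies blocked randomisation at 1:1:1 and states that "The block size of 6 will be used". A team member who takes no part in enrolment or outcome assessment generates the list, which is concealed in opaque, sealed, sequentially numbered envelopes. The person opening an envelope signs it and records the date and time. Principal and sub-investigators screen and enrol, and "Principal Investigator and/or Sub Investigator will assign the treatment to each subject, according to the allocation sequence". Section 8.1 describes an "open-label, randomised, parallel-group study to compare the efficacy", so past allocations are visible to site staff.

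On the division among the three sites, the plan gives only hints. The front of each envelope carries "Site name and code", which suggests that each site has its own run. Section 8.3 gives each subject a "sequentially numbered study identifier according to the order in which he or she is enrolled in the trial", which could point to a single list. Neither wording is decisive, and section 11.1.3 only repeats the envelope method.

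**The concern.** Opaque envelopes and an independent generator hide the list. They do not hide what can be deduced from visible allocations when the block size is known: a block of 6 holds two of each arm, so its end can be worked out from its beginning.

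Foreknowledge matters only if staff can act on it, and some room remains before randomisation:

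- Eligible patients "will be called up for a baseline visit no longer than 1 weeks from screening visit", so the day of randomisation is flexible within that week (section 11.1.2).
- One exclusion rests on judgement: "Inability or unwillingness to comply with the requirements of the protocol as determined by the investigator" (section 8.4.2).
- Prognosis can vary among eligible patients. Free T4 has a lower limit for entry but no upper limit, and section 8.4.1 admits patients "who are either newly diagnosed or previously diagnosed and receiving ATDs currently".
- The primary comparison in section 13.2.2 is an unadjusted Z test, so the analysis would not absorb a selected imbalance.

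At stake is the comparability of the arms at entry. Central hormone assays protect measurement of the outcome but not the choice of who is randomised when.

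**Working it through.** The plan gives no calculation behind the block size, so there is no figure of its own to reproduce.

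**Inputs.** From the documents: block of 6, three arms at 1:1:1, three sites, 135 patients, and up to one week from screening to baseline. Assumed: 135/3 = 45 patients per site, and an observer who knows the block size and every earlier allocation at the site.

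**1. Certainty at randomisation, each site with its own run.**
- A block has 6!/(2!·2!·2!) = 90 orders. The sixth allocation is always known.
- The fifth is known only if the last two are the same arm: 3 × 4!/(2!·2!) = 18 orders, and 18/90 = 0.2.
- Positions 1-4 are never certain. Complete blocks: (0.2 + 1)/6 = 20%.
- 45 patients make 7 complete blocks and 3 over: 7 × 1.2 = 8.4, and 8.4/45 = 18.7%.
- One list of 135 cut into consecutive site runs (1,500 simulated lists) gives about 18.7% at 45/45/45, and 16-20% for runs of 50/45/40 or 60/45/30.

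**2. Certainty at invitation.** Other patients may be randomised in the gap.
- With one in between, only the sixth allocation can be known, with probability 0.2: 7 × 0.2/45 = 3.1%. With two or more, nothing is certain.
- Let the number in between be Poisson with mean m, its value assumed known to the observer: P = e^(−m) × (0.187 + 0.031m).
- Assumed site rates: 45 over 34.9 weeks (1 May to 31 December 2017) = 1.29 a week; 45 over 23.9 weeks (5 June to 19 November, so that week 6 ends by 31 December) = 1.89 a week.

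| Gap and rate | m | Certain |
|---|---|---|
| Full week, 1.3 a week | 1.3 | 6.2% |
| Full week, 1.9 a week | 1.9 | 3.7% |
| Half week, 1.3 a week | 0.65 | 10.8% |

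**3. All sites interleaved on one list, staff seeing only their own patients.** Let s be the site's share of patients. Certainty requires that the four allocations to the other two arms all came earlier in the block and all at that site, so P = 0.2 × s^4, even if envelope numbers reveal list position. For s = 1/3: 0.2/81 = 0.25%. For s = 1/2: 0.2/16 = 1.25%.

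**4. Varied blocks.** Simulated lists of 45, with an observer who knows the set of sizes but not their order and updates after each allocation:

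| Block sizes | Certain | Best guess correct |
|---|---|---|
| 6 only | 18.7% | 55% |
| 3, 6 | 8.5% | 57% |
| 6, 9 | 4.9% | 54% |
| 6, 9, 12 | 2.4% | 52% |

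The best guess for fixed blocks can be checked by hand. Over positions 1-6 it is 1/3, 2/5, 1/2, 8/15, 3/5 and 1, which sum to 3.367. Then (7 × 3.367 + 1.233)/45 = 55%, where 1.233 is the sum for the three left-over positions. Chance is 33%. Including blocks of 3 makes guessing slightly easier than fixed 6.

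**5. Imbalance.** An incomplete last block can leave two arms at a site differing by at most 2 with size 6, or 4 with size 12. Over three sites that is 6 or 12.

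**The case against.** The strongest case against is that this is a design preference. The list generator is independent; envelopes are opaque, numbered, signed and timed; and treatment is revealed only on the first treatment day. Screened patients are logged (section 8.4.6), entry has a laboratory threshold, baseline thyroid tests are run centrally (section 11.1.2), and baseline characteristics are compared by arm (section 13.2.1). Marked selection could therefore be seen afterwards. Consent and the eligibility check come at screening, when foreknowledge is low, and a patient who qualifies and completes baseline is randomised the same day. All of this stands, and it is why the point is minor.

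The remedy also does less than the fall in certain predictions suggests. A reader might infer that cutting them about eightfold cuts any bias about eightfold. That would hold only if staff acted solely when certain. Suppose instead that they acted on any lean towards or away from control, choosing patients 10 percentage points better or worse than average (an assumption, not a figure from the documents). The simulated shift in the arm difference is then about 7.7 points with fixed blocks and 6.6 with sizes 6, 9 and 12, a reduction of 1 − 6.6/7.7 = 14%.

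It is also fair to say that the whole size depends on an unstated fact, the division among sites. That does not remove the point, because the missing statement is part of it.

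**Conclusion.** The point holds as a cheap improvement of minor severity. One printed block size, open treatment and investigators who both enrol and assign make some allocations deducible, and the unstated division among sites decides how many. The range runs from about 0.25% (interleaved list, equal sites) to about 19% (own runs, at randomisation), with about 4-11% at invitation for own runs. Site labels on the envelopes make own runs the likelier reading but do not prove it. These figures are upper bounds: they assume 45 per site, a diligent observer and, at invitation, the stated recruitment rates.

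A reader might go further and infer that concealment fails, that selection bias will occur, or that type I error is inflated by a definite amount. The documents do not support this. They give no evidence of selection, and no figure for how far staff would act on a prediction or how different the chosen patients would be.

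**What to change.** 1. Remove the block size from the protocol held at sites, and keep it in a restricted document held by the person who generates the list.
2. State in section 9.4 whether there is one list or one per site, and how envelopes are divided among the three sites.
3. If sites hold their own runs, whether from separate lists or from one list cut up, generate the unused allocations as site lists with randomly ordered block sizes, for example 6, 9 and 12, avoiding blocks of 3. Replace only unopened envelopes and keep all allocations already made. If a central mechanism truly interleaves all sites on one list, steps 1 and 2 are enough.

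The cost is an amendment approved by the ethics committee (sections 5.1 and 14.4), a new list and new envelopes for unused allocations, and the larger possible imbalance in step 5 of the working. Sample size, endpoint and analysis do not change. If enrolment has begun, staff already know the old block size, so only allocations from the new list benefit.
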